2.5 Study Objectives

Primary objective:

- Determine the safety and toxicological profile of plitidepsin at each dose level administered according to the proposed administration schedule in patients admitted for COVID-19.

Secondary objectives:

- Evaluate the efficacy of plitidepsin in COVID-19 patients at proposed dose levels by:
 - Change in SARS-CoV-2 viral load from baseline
 - Time to negative detection of SARS-CoV-2 by PCR.
 - Cumulative incidence of disease severity. It will be evaluated by:
 - Deaths
 - Need for invasive mechanical ventilation and/or ICU admission
 - Need for non-invasive mechanical ventilation
 - Need for oxygen therapy
- Selection of the recommended dose levels of plitidepsin for conducting a phase II/III efficacy study.

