- Time to Hospital discharge (continuous): The time to Hospital discharge is defined as the time, in days, from the date of treatment start and the date of hospital discharge. In those patients who have not been discharged, the time, in days, from the date of first dose to the last available date will be calculated and it will be censored for time to event analyses. The description of the variable will be done separately depending on whether the patient has been discharged from hospital or not. The median and 95% confidence interval will be presented.
- Time from admission to Hospital discharge (continuous): The time to Hospital discharge is defined as the time, in days, from the date of admission and the date of hospital discharge
- Multivariate analysis will be done to evaluate the relationship of the main covariates in the analysis with Hospital discharge on Day 8 (Yes/No) and Hospital discharge on Day15 (Yes/No) by means of logistic regression models. More relevant exploratory covariates from the univariate analyses (p-value < 0.10) will be included in the multivariate analyses.
- Multivariate analysis will be done to evaluate the relationship of the main covariates in the analysis with time to hospital discharge by means of Cox proportional hazard models. More relevant exploratory covariates from the univariate analyses (p-value < 0.10) will be included in the multivariate analyses.
- Swimmer plot Hospital Discharge Day by Viral Load at Baseline, Disease Severity at Baseline and oxygen (yes/no) at baseline.

m) Class at discharge:

The time to hospital discharge (category 1) at 6-points ordinal scale will be analyzed by the Kaplan-Meier method and the median and the 95% confidence interval will be provided.

The analysis will be completed by the following subgroups:

- FDA classification
- Oxygen therapy on day 1
- Symptoms evolution less or equal/greater than 6 days.

The value of the 6-point ordinal scale will be derived from CRF data by using the following definition:

1. Discharge (Alive)
2. Hospital admission, not requiring supplemental oxygen.
3. Hospital admission, requiring supplemental oxygen.
4. Hospital admission, requiring high-flow nasal cannula or non-invasive mechanical ventilation.
5. Hospital admission, requiring extracorporeal membrane oxygenation or invasive mechanical ventilation.
6. Death.

In addition, the following analyses will be performed:

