APPENDIX III

12 EFFICACY EVALUATION

12.1 Efficacy evaluation

Table 12.1.1 Number of patients with PCR

Number of patients with PCR	Dose Cohort			
	1.5 mg N=X	2.0 mg N=X	2.5 mg N=X	Total N=X
Baseline				
Undetectable				
Positive				
Day ...				

Table 12.1.2 Viral load classification by dose level and total

Day	Viral Load at baseline (copies/mL)	Viral Load classification during treatment (copies/mL)			
		Low <4	Medium [4-7]	High >7	Total
Day 4	Low <4				
	Medium [4-7]				
	High >7				
	Total				
...(*)	Low <4				
	Medium [4-7]				
	High >7				
	Total				

(*) Days 7, 15 and 31

Listing 12.1.3 Viral load evolution

Subject id	Dose	Visit	Result	log10 viral load copies/mL

Table 12.1.4 Summary of Protocol-Specified Efficacy Endpoints. Cumulative results.

Endpoint from day 1 to	Dose Cohort			
	1.5 mg N=X	2.0 mg N=X	2.5 mg N=X	Total N=X
Patients discharged from hospital, n (%)				
Day 7				
Day 8				
Day 15				
Day 31				
Deaths at, n (%)				
Day 7				
Day 15				
Day 31				
Later than Day 31				
Patients requiring invasive mechanical ventilation and/or ICU admission at, n (%)				
Day 7				
Day 15				
Day 31				
Patients requiring invasive mechanical ventilation, n (%)				
Day 7				
Day 15				
Day 31				
Patients requiring ICU admission at, n (%)				
Day 7				
Day 15				
Day 31				
Patients requiring non-invasive mechanical ventilation at, n (%)				
Day 7				
Day 15				
Day 31				
Patients requiring oxygen therapy at, n (%)				
Day 7				
Day 15				
Day 31				
Patients requiring oxygen therapy (high flow) at, n (%)				
Day 7				
Day 15				
Day 31				
Patients requiring oxygen therapy (low flow) at, n (%)				
Day 7				
Day 15				
Day 31				

This table will be also performed by age (<65 vs. ≥65 year old (12.1.4.1)

This table will be also performed by FDA classification (12.1.4.2)

Table 12.1.5 Summary of Protocol-Specified Efficacy Endpoints. Non-cumulative results.

Endpoint	Dose Cohort			
	1.5 mg N=X	2.0 mg N=X	2.5 mg N=X	Total N=X
Patients discharged from hospital, n (%)				
Day 1 to Day 8				
Day 9 to Day 15				
Day 16 to Day 31				
Deaths at, n (%)				
Day 1 to Day 7				
Day 8 to Day 15				
Day 16 to Day 31				
Later than Day 31				
Patients requiring invasive mechanical ventilation and/or ICU admission at, n (%)				
Day 1 to Day 7				
Day 8 to Day 15				
Day 16 to Day 31				
Patients requiring invasive mechanical ventilation, n (%)				
Day 1 to Day 7				
Day 8 to Day 15				
Day 16 to Day 31				
Patients requiring ICU admission at, n (%)				

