APPENDIX V

15 Additional figures with R software

Some additional descriptive figures performed with R are added as supportive analyses.

An outcome classification (good or poor) will be used to compare in this section these subgroups.

This classification will be calculated as follow:

- Good outcome: Patients alive and Discharged before day 9
- Poor outcome: Patients death or not discharge before day 9

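### Hospital discharge is in no endpoint list but opens two tables titled as protocol-specified; its models screen covariates at p < 0.10 on at most 22 rarer outcomes, and its Kaplan-Meier analysis censors deaths

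*SAP*

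**What the plan says.** **Endpoint lists.** The protocol's secondary objectives (1.8, 5.3), secondary endpoints (1.11, 6.3) and efficacy analyses (12.5.1) cover viral load, time to negative PCR, death, invasive ventilation and/or ICU admission, non-invasive ventilation and oxygen therapy. SAP 2.5 repeats the clinical part under "Cumulative incidence of disease severity. It will be evaluated by", followed by deaths, ventilation and ICU, and oxygen. SAP 2.6 follows the same pattern. Discharge is in none of these lists.

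**Tables.** SAP Appendix III has "Table 12.1.4 Summary of Protocol-Specified Efficacy Endpoints. Cumulative results" and "Table 12.1.5 Summary of Protocol-Specified Efficacy Endpoints. Non-cumulative results". The first block of each is "Patients discharged from hospital, n" (%). Only for discharge does Day 8 close a reporting window. Table 12.1.4 gives discharge a Day 8 row, and in Table 12.1.5 its first interval ends on Day 8. The other endpoints reported by interval have a first interval ending on Day 7.

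**Models.** SAP 8.1 l plans logistic models for discharge by Day 8 and by Day 15, and a Cox model for time to discharge. The covariate rule is "More relevant exploratory covariates from the univariate analyses (p-value < 0.10) will be included in the multivariate analyses". There is no candidate list and no cap on the number of terms.

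**Time to discharge.** For patients not discharged, the time from "the date of first dose to the last available date will be calculated and it will be censored for time to event analyses". Death has no separate rule. SAP 8.1 m adds: "The time to hospital discharge (category 1) at 6-points ordinal scale will be analyzed by the Kaplan-Meier method", with a median and 95% confidence interval.

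**The concern.** There are three separate faults.

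1. The table title is untrue for its first block. A reader of the report could take discharge for an endpoint that the protocol set.
2. Choosing covariates by their own p-values from an unlisted pool, in 45 patients, tends to put noise into the model. The noise that gets in carries a sizeable odds ratio, because only sizeable estimates pass. If dose enters, its contrast is too imprecise to help choose a dose.
3. A patient who dies cannot later be discharged. Kaplan-Meier treats a censored patient as someone who still could be, so the discharge curve is too high whenever a death comes before later discharges.

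**Working it through.** **Size of the analysis set.** SAP sections 1 and 2.4 give 27 + 18 = 45 patients, that is 3 x 15. This reproduces the plan's total.

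**Ceiling on information.** For a yes/no outcome the rarer category holds at most floor(45/2) = 22 patients. This needs no knowledge of the results. The efficacy population may be smaller: 42 patients would give 21 and 40 would give 20. It could also slightly exceed 45. Protocol 8.3 replaces some patients who stop treatment early, while 12.3 keeps those who stopped because the disease worsened. Each two extra patients raise the ceiling by one. As a working assumption of ten rarer outcomes per coefficient, 22/10 = 2.2, so about two terms.

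**The p < 0.10 screen.** The number of candidates is not given, so I assume k = 5 or 10, all unrelated to discharge.

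- Independent tests: P(at least one passes) = 1 - 0.9^k, which is 1 - 0.590 = 41% for k = 5 and 1 - 0.349 = 65% for k = 10.
- Simulation: 45 patients, null standard-normal covariates, univariate logistic likelihood-ratio test at 0.10, 1,000 replicates per setting. The counts of 12 and 8 rarer outcomes are assumptions.

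| Rarer outcomes | At least one passes, k = 5 | k = 10 | Median OR per SD of a passing noise covariate (taken as > 1) |
|---|---|---|---|
| 22 | 44.6% | 69.6% | about 1.9 |
| 12 | 44.8% | 67.9% | about 2.1 |
| 8 | 44.0% | 68.6% | about 2.4 |

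**Dose contrast, if dose enters.** SAP 8.1 l does not name dose as a term. The best case is 22 rarer outcomes spread evenly, 22/3 = 7.33 per arm against 15 - 7.33 = 7.67. For the unadjusted 2.5 vs 1.5 mg log odds ratio:

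SE = sqrt(2 x (1/7.33 + 1/7.67)) = 0.73

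Ratio of upper to lower 95% limit = exp(2 x 1.96 x 0.73) = about 17.5

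Fewer rarer outcomes, or added covariates, would generally widen this.

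**Censored deaths.** The number of deaths is not given. If d patients in an arm of 15 die before the last discharge and all others are discharged, the last patient at risk is discharged and one minus Kaplan-Meier ends at 100%. The true proportion is (15 - d)/15:

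- d = 1: 14/15 = 93.3%
- d = 2: 13/15 = 86.7%
- d = 3: 12/15 = 80.0%

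Over all 45 patients, with d = 1 to 5, the true proportion is 44/45 = 97.8% down to 40/45 = 88.9%, again against 100%. Part-way along the curve, with d early deaths and 30 discharges so far, one minus Kaplan-Meier is 30/(45 - d), or 68%, 70%, 71% and 75% for d = 1, 2, 3 and 5. The true figure is 30/45 = 67%.

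**The case against.** Much of the other side stands.

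- **Low stakes.** SAP section 1 calls the analyses descriptive, 8.1 l calls the covariates exploratory, the primary objective is safety, and no stated rule uses these models. Protocol 12.1 lets the SAP add analyses, so adding discharge is allowed. Only the title is wrong.
- **Deaths are partly covered.** Table 12.1.4 gives crude proportions discharged and dead by fixed days over the arm total. With complete follow-up, this is the competing-risk proportion. Table 12.1.32 gives the full ordinal scale, death included. The Kaplan-Meier median is unchanged if deaths come after half are discharged. The Cox model remains a valid cause-specific hazard model. The yes/no models count a death before discharge as not discharged. What is left is the plotted curve, and the median if deaths come early.

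Four stronger readings are tempting, but the documents do not support them.

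- **That discharge was added after the data were seen.** Appendix V prints numbers, but the text does not say what they are or when discharge was chosen.
- **That the planned model has six slopes.** Figure 15.4.1 prints six coefficients, but 8.1 l fixes no number. Under the null screen above, on average about 0.5-0.6 of 5 or 1.1-1.2 of 10 candidates pass.
- **That Figures 15.1.2 and 15.4.1 conflict, or that Day 15 leaves a single undischarged patient.** Both claims read the counts under Figure 15.1.2 as patients at risk by day. The plot is not in the text available here, the column labels carry no unit, and the event coding, data set and fitting method of Figure 15.4.1 are not stated.
- **That censoring deaths contradicts the scale.** Death is category 6, but the event analysed is category 1, so the two are consistent. The Appendix V grouping, "Poor outcome: Patients death or not discharge before day 9", is a separate binary classification.

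**Conclusion.** The concern holds at low weight: worth fixing, but not a threat to the trial's primary purpose.

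- **Label.** The mismatch is certain and needs no assumption.
- **Models.** The ceiling of 22 follows from 45 patients alone. The chance of a false pass (about 41-45% or 65-70%) depends on the assumed 5 or 10 unrelated candidates. The 17.5-fold interval is a best case and applies only if dose is a term.
- **Deaths.** That they are censored follows from the general rule for undischarged patients. The direction of the bias is certain whenever a death precedes later discharges. Its size (100% against 93-80% in an arm of 15) rests on 1 to 3 assumed deaths and may be negligible if there are few or none.

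**What to change.** 1. Move discharge out of Tables 12.1.4 and 12.1.5, or retitle them. State in SAP 2.6 and in 8.1 l and m that discharge is an exploratory endpoint added by the SAP.
2. Replace the p < 0.10 screen with one or two named terms, fitted by Firth's penalised likelihood and reported with confidence intervals. Three-level dose alone uses two coefficients. Fit the Day 15 model only if the count in its rarer category supports it, and say what count that is. Limit the Cox model in the same way.
3. Show time to discharge as an Aalen-Johansen cumulative incidence with death as a competing event. Alternatively, keep patients who die in the risk set to Day 31 as not discharged.
4. State in Figure 15.4.1 which outcome is modelled, discharge or non-discharge.

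The cost is new titles and minor re-programming, with no new data. The modelled estimates will look less striking.

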9 LISTINGS

The following data listings will be provided by patient and treatment arm for the total sample of patients included in the database.

9.1 Demographics, symptoms, and comorbidities data

The listing "Demographic, symptoms and comorbidities" will include the following information:

- Center
- Patient id.
- Dose.
- Age (years)
- Gender (Male/Female).
- Ethnic group
- Time from onset of first symptom
 - to hospital admission
 - to the administration of the first dose of plitidepsin
- Time from hospital admission to administration of the first dose of plitidepsin
- Fever history (Yes/No)
- Dehydration (Yes/No).
- Cough (Yes/No). In affirmative case, describe:
 - Sputum production (Yes/No). In affirmative case, describe:
 - Bloody sputum/ Hemoptysis (Yes/No).
- Runny nose (rhinorrhea) (Yes/No).
- Earache (Yes/No).
- Crackles (Yes/No).
- Thoracic pain (Yes/No).
- Muscular pain (myalgia) (Yes/No).
- Joint pain (arthralgia) (Yes/No).
- Fatigue / malaise (Yes/No).
- Short of breath (dyspnea) (Yes/No).
- Intercostal retraction (Yes/No).
- Headache (Yes/No).
- Altered state of consciousness / confusion (Yes/No).
- Convulsion (Yes/No).
- Abdominal pain (Yes/No).

- Vomiting / nausea (Yes/No).
- Diarrhea (Yes/No).
- Conjunctivitis (Yes/No).
- Rash (Yes/No).
- Skin ulcers (Yes/No).
- Lymphadenopathy (Yes/No).
- Throat pain (Yes/No).
- Bleeding (hemorrhage) (Yes/No). If so, the description of the bleeding locations will be detailed.
- Chronic cardiac pathologies including congenital cardiac pathologies (does not include hypertension) (Yes / No).
- Arterial hypertension (Yes/No).
- Chronic lung disease (does not include asthma) (Yes/No).
- Asthma (medical diagnosis) (Yes/No).
- Diabetes with complications (Yes/No).
- Diabetes without complications (Yes/No).
- Chronic kidney disease (Yes/No).
- Rheumatic disorder (Yes/No).
- Moderate or severe liver disease (Yes / No).
- Mild liver disease (Yes/No).
- Dementia (Yes/No).
- Malnutrition (Yes/No).
- Chronic neurological disorder (Yes / No).
- Smoker (Yes/No).
- Malignant neoplasm (Yes/No).
- Chronic hematological disease (Yes / No).
- AIDS / HIV (Yes / No).
- Obesity (define by medical staff) (Yes/No).
- Other risk factors (Yes / No). If so, the description of the specified factors will be detailed.
- SBP (mmHg) (continuous).
- DBP (mmHg) (continuous).
- Heart rate (b.p.m.) (continuous).
- Respiratory rate (b.p.m.) (continuous).
- Temperature (°C) (continuous).
- Saturation O₂ (%) (continuous).
- Saturation (Room air/Oxygen therapy/Not available). In the case of oxygen therapy, the following will be described:

- Oxygen therapy type (Nasal glasses; Simple mask; Venturi mask; Reservoir mask; Other). In case of other a detailed listing will be provided.
- Flow (L/min) (continuous).
- FiO₂ (%) (continuous).
- PaO₂ (mmHg) (continuous)
- PaO₂/FiO₂ o SaO₂/FiO₂ (continuous).
- Chest X-ray (Yes/No). if so, the following will be described:
- X-ray result (Normal/Abnormal). In case of abnormality, the abnormality will be detailed (Unilateral Pneumonia / Bilateral Pneumonia / Other). In case of other abnormality, the description of the abnormalities will be provided.
- Electrocardiogram (Yes / No). If so, it will be described:
- Result (Normal / Abnormal: Not clinically significant or Abnormal: clinically significant). In case of abnormality, the description of the abnormalities will be provided. (QT interval prolongation / PR interval prolongation / other alteration). In case of other alteration, the description of the other alteration will be provided.

9.2 Screening failure

The listing "Screening failure" will include the following information

- Center
- Patient id.
- Screening failure (yes/no)
- Reason for selection failure (Inform consent withdrawal; Administration of prohibited medication; Death; Failure to comply with selection criteria).
 - Specific criteria, in case of the reason for selection failure is non-compliance with selection criteria.

9.3 Treatment

The listing "Treatment" will include the following information:

- Center
- Patient id.
- Treatment arm (Arm A; Arm B; Arm C)
- Treatment administration (Yes/No).
 - If so, reasons will be detailed.
- Administered doses
- Treatment interruption (Yes/No).
 - If so, the reasons will be indicated.
- Pre-medication (Yes/No). If so, it will be indicated:
 - Type (antiemetic, gastric protector, antihistamine and corticosteroids)
 - Code (ATC)

- Active substance
- Dose
- Route of administration
- Units
- Days on treatment with plitidepsin
- Total dose of plitidepsin administered (sum of daily doses - mg)
- End of treatment date
- End of treatment (Treatment completed according to protocol; Withdraw informed consent; Non related adverse event; Adverse reaction to plitidepsin; Death; Investigator's decision; Administration of prohibited medication; Other).
 - If the adverse event is not related to the drug, the description of event and grade will be provided (1; 2; 3; 4; 5; Not available).
 - If the adverse event is related to the drug, the description of event and grade will be provided (1; 2; 3; 4; 5; Not available).
 - If it is Investigator's decision: specify
 - If other: specify

9.4 Adverse events

The listing “Adverse events” will include the following information:

- Center
- Patient id
- Treatment arm (Arm A; Arm B; Arm C)
- Age (<65 years; ≥ 65 years)
- Number of the adverse event
- Original term
- System (SOC)
- Preferred term (PT)
- Grade (1; 2; 3; 4; 5)
- Seriousness (Yes/No)
- Start date
- Ongoing
- End date
- Action taken (None; Treatment interruption; dose omitted; treatment withdrawal; Unknown)
- Relationship (Plitidepsin; Concomitant medication; Concomitant procedure; Related with study disease; Related with other disease; Other; Unknown)
 - Concomitant medication: specify.
 - Concomitant procedure: specify.
 - Related with other disease: specify.
 - Other: specify.

- Outcome (Recovered; Recovered with sequelae; Not recovered / Continues; Unknown; Death)
- Severity criteria (Death; Life-threatening; Requires hospitalization / Prolongation of hospitalization; Permanent or significant disability; Congenital anomaly or birth defect; Important medical event; transmission of an infectious agent via a medicinal product).
- Onset day: It is defined as the time, in days, from the start of treatment with plitidepsin to the date of onset of the adverse event. It will be specified for those adverse events related to plitidepsin.
- For plitidepsin-related adverse events of nausea or vomiting, additional information will be included regarding whether the patient exhibited such symptoms at the baseline visit and the administration of antiemetic prophylaxis at each of the plitidepsin doses.

9.5 Laboratory parameters

The listing “Laboratory parameters” will include the following information for baseline visit and day 3, 7, 15 y 31 visits. The units, the percentage change from baseline and the result of each parameter will be specified. In the visit where the parameter is above the normal limit or below the normal limit is indicated, the clinically significant variable will be specified. Parameters will be standardized to equivalent units prior to data analysis.

- Center
- Patient id.
- Treatment arm (Arm A; Arm B; Arm C)
- Visit (Baseline, Day 3, Day 7, Day 15, Day 31)
- Date.
- Hematology:
 - Erythrocytes and units
 - Erythrocytes % change vs. Baseline
 - Hemoglobin and units
 - Hemoglobin % change vs. Baseline
 - Hematocrit and units
 - Hematocrit % change vs. Baseline
 - Platelets and units
 - Platelets % change vs. Baseline
 - Leukocytes and units
 - Leukocytes % change vs. Baseline
 - Neutrophils and units
 - Neutrophils % change vs. Baseline
 - Lymphocytes and units
 - Lymphocytes % change vs. Baseline
 - Lymphocytes-neutrophils relation
 - Lymphocytes-neutrophils % change vs. Baseline
 - Monocytes and units
 - Monocytes % change vs. Baseline

- Eosinophils and units
- Eosinophils % change vs. Baseline
- Basophils and units
- Basophils % change vs. Baseline
- Coagulation:
 - APTT/PTT and units
 - APTT/PTT % change vs. Baseline
 - PT and units
 - PT % change vs. Baseline
 - INR
 - D-dimer and units
 - D-dimer % change vs. Baseline
- Biochemistry:
 - Glucose and units
 - Glucose % change vs. Baseline
 - Alkaline phosphatase and units
 - Alkaline phosphatase % change vs. Baseline
 - Total Bilirubin and units
 - Bilirubin % change vs. Baseline
 - ALT and units
 - ALT % change vs. Baseline
 - AST and units
 - AST % change vs. Baseline
 - GGT and units
 - GGT % change vs. Baseline
 - LDH and units
 - LDH % change vs. Baseline
 - Creatinine and units
 - Creatinine % change vs. Baseline
 - CPK and units
 - CPK % change vs. Baseline
 - Ferritin and units
 - Ferritin % change vs. Baseline
 - Troponin and units
 - Troponin % change vs. Baseline
 - C-reactive protein and units

- C-reactive protein % change vs. Baseline

9.6 Other COVID-19 treatments

The listing “Other COVID-19 treatments” will include the following information including the baseline visit

- Center
- Patient id.
- Treatment arm (Arm A; Arm B; Arm C)
- COVID-19 Pharmacological treatment (Yes/No). If so, it will be described:
 - Chloroquine / Hydroxychloroquine (Yes / No).
 - Tocilizumab (Yes/No).
 - Remdesivir (Yes/No).
 - Lopinavir/Ritonavir (Yes/No).
 - IFN B 1b (Yes/No).
- Other pharmacological treatment (Yes/No). If so, a list per patient will be provided.
- Support treatment (Yes/No). If so, it will be described:
 - Antibiotics (Yes/No). If so, it will be described:
 - Azitromizina (Yes/No).
 - Other (Yes/No). If so, the specific treatment will be described
 - High-dose corticosteroids (excluding pre-medication) (Yes/No). If so, the specified treatment description will be described.
 - Antifungal agents (Yes / No). If so, the description of the specified treatment will be described.
 - Other support treatments (Yes / No). If so, the description of the specified treatment will be described.

Note: Information will only be provided for those patients receiving other COVID-19 drug treatment and/or supportive treatment at those visits where indicated.

The active substances provided will be coded including code (ATC) and term indicated in the database.

In the case of another pharmacological treatment for COVID-19 and/or support treatment with high-dose corticosteroids drugs, information about the time, in days, since the start of treatment with plitidepsin and the start of the other therapy, and the duration of the treatment will be provided

For corticosteroids, the daily dose received data will also be provided.

